5.7 Radiation specifications

This protocol requires photon external beam radiation therapy (EBRT), either 3D conventional radiation therapy (3D- CRT) or intensity modulated radiation therapy (IMRT) techniques followed by low dose rate (LDR) or high dose rate (HDR) brachytherapy. Radiation therapy must be completed within 60 days of initiation. Four-field box 3D-CRT and IMRT are pretreatment stratification variables.

- For 3D-CRT, the prescription dose is 45 Gy in 25 fractions at 1.8 Gy/fraction with an optional parametrial boost of 5.4 Gy in three fractions at 1.8 Gy/fraction. EBRT should be given once daily Monday-Friday, 5 fractions per week.
- For IMRT, the prescription dose is 45 Gy in 25 fractions at 1.8 Gy/fraction, unless a simultaneous integrated boost (SIB) is used for gross nodal disease. For SIB cases, the primary target will receive 47.6 Gy in 1.7 Gy/fraction and the gross nodal PTV (PTV_Boost) will receive 1.93-2.12 Gy per fraction, depending on bowel tolerance. IMRT should be given once daily Monday-Friday, 5 fractions per week.
- For brachytherapy, the prescription doses are 27.5 - 30 Gy for HDR.

Cohort 1A - Extended-Field Radiation Therapy (EFRT) - EFRT will be used for patients with any positive common iliac LN requiring extension of the superior border of the radiation field above the L4-L5 inter-space as detailed in Section 5.7.1.

Cohort 1B -Whole Pelvic Radiation Therapy (WPRT) - WPRT will be used for patients without evidence of high common iliac LN necessitating EFRT. The traditional whole pelvic radiation field borders are as detailed in Section 5.7.1.

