Pelvic Tumor Volume (PTV)	Required dose = 45 Gy	Around CTV1, a 15 mm uniform expansion should be used. Around CTV2, a 10 mm uniform expansion should be used. Around CTV3 (and CTV_boost, if applicable), a 5 mm uniform expansion should be used. These expansions will generate PTV1, PTV2, and PTV3, respectively. PTV1-3 will be fused to generate the PTV .
PTV-skin	IF applicable only: PTV-3mm from skin surface	The PTV should be manually or automatically trimmed up to 3 mm from the skin surface, if necessary, to spare skin. However, the CTV still needs to be included entirely within the PTV .
PTV-boost	Required dose = 54 to 59.4 Gy	5 mm uniform expansion around CTV_Boost

Brachytherapy (point-directed)

The definition of all points (A, B, Bladder, Rectum and Vaginal Surface) will be in accordance with the 1985 ICRU Report #38: Dose and Volume Specifications for Reporting Intracavitary Therapy in Gynecology.

BrUOG 355: 7/8/17, 7/11/17, 7/20/17, 8/7/17, 8/8/17, 8/14/17, 8/16/17, 8/21/17, 8/22/17, 8/24/17, 8/28/17, 9/5/17, 9/6/17, 9/8/17, 9/11/17, 11/7/17, 11/8/17, 11/19/17 approved DD, 11/20/17, 12/12/17, 12/14/17, 1/29/18, 2/1/18, 2/6/18, 2/7/18, 2/8/18, 2/9/18, 2/12/18, 2/13/18, 3/8/18 all reviews, 3/9/18, 3/13/18, 3/14/18, 3/15/18, 4/19/18, 4/23/18, 5/29/18, 6/5/18, Amendment # 1 7/9/18, Amendment # 2 12/12/18, Amendment #3, 4/6/2020, Amendment #4 5/11/2020

Brachytherapy (volume-directed)

The MRI based target delineation can be reused by superimposition in the process of contouring on CT, if for subsequent fractions of brachytherapy only CT can be used with the applicator in place. No planning margins will be added to the CTV.

Standard name	Description	Specification
GTV	Required dose = 27.5-30 Gy	Macroscopic tumor (if present) at time of brachytherapy
CTV		GTV + whole cervix + presumed extra cervical tumor extension

Compliance criteria:

	Per protocol	Variation (Acceptable)	Deviation (Unacceptable)*
Overall Treatment time	≤ 60 days	≤ 66 days	>66 days

Patients who require a treatment delay of RT for 7 consecutive days or longer will be removed from this protocol. The decision to continue standard chemoradiation will be left to the treating physician. See Section 6.2.

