5.7.5 Dose Prescription

Conventional RT

For Conventional RT, the prescription dose of 45 Gy at 1.8 Gy/fraction will be delivered to the isocenter which is defined as the intersection of the four beams. EBRT is preferably given once daily Monday-Friday, for 5 fractions per week. A three consecutive day parametrial boost may be optionally given in the sixth week.

IMRT

Standard	Dose (Gy)	Fraction size (# fractions)	Technique
PTV	45	1.8 (25)	Exactly 95% of PTV receives ≥ 45 Gy
PTV (for SIB)	47.6	1.7 (28)	Exactly 95% of PTV receives ≥ 47.6 Gy
PTV boost (for SIB)	54.0-59.4	1.93-2.12 (28)	Exactly 95% of PTV receives $\geq 54=58.4$ Gy

Parametrial boost.

After the delivery of 45 Gy, at the discretion of the treating physician, a parametrial boost of 5.4 Gy at 1.8 Gy/fraction may be delivered to mid-plane given by AP/PA fields and the center of the unblocked portion of the field.

Lymph Node Boost

After the delivery of 45 Gy WPRT/EFRT +/- parametrial boost, a nodal boost may be delivered to any grossly positive lymph node (PET SUV > 2.5, LN > 15mm short axis diameter on CT/MRI, or histologically positive). Nodal boosts should be delivered to a final dose of 54-59.4 Gy in keeping with bowel tolerance at the discretion of the treating physician.

HDR Brachytherapy

In point-directed approach, the doses of 27.5 - 30 Gy and 35 - 40 Gy will be delivered to the point A for HDR. The HDR brachytherapy dose can be prescribed to a high-risk clinical target volume (CTV) as volume-directed approach, but point A dose must be documented.

Total EBRT (Gy)	# Fractions	HDR Point A dose/fraction (Gy)	Total HDR point A Dose (Gy)	Total Point A EQD2-Gy ₁₀
45	4	7	28	83.9
45	5	5.5	27.5	79.8
45	5	6	30	84.3
47.6	4	7	28	86.1
47.6	5	5.5	27.5	81.9
47.6	5	6	30	86.4

HDR-Point A determined implant or volume directed approach

BrUOG 355: 7/8/17, 7/11/17, 7/20/17, 8/7/17, 8/8/17, 8/14/17, 8/16/17, 8/21/17, 8/22/17, 8/24/17, 8/28/17, 9/5/17, 9/6/17, 9/8/17, 9/11/17, 11/7/17, 11/8/17, 11/19/17 approved DD, 11/20/17, 12/12/17, 12/14/17, 1/29/18, 2/1/18, 2/6/18, 2/7/18, 2/8/18, 2/9/18, 2/12/18, 2/13/18, 3/8/18 all reviews, 3/9/18, 3/13/18, 3/14/18, 3/15/18, 4/19/18, 4/23/18, 5/29/18, 6/5/18, Amendment # 1 7/9/18, Amendment # 2 12/12/18, Amendment #3, 4/6/2020, Amendment #4 5/11/2020

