In general, HDR insertions should start during the fourth week and be separated by a minimum of 48 hours and no more than 2 insertions should be performed per week. Iridium-192 is the preferred source for HDR brachytherapy. External beam radiation and brachytherapy may not be administered on the same day. Radiation therapy must be completed within 6 weeks of its initiation.

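### Radiation therapy has two mandatory completion limits, 6 weeks and 60 days; 28 fractions plus weekday HDR cannot fit in 6 weeks, and section 16.1.1 leaves its 8-week clock undefined

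*Combined protocol and SAP*

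**What the plan says.** Three places in the current text limit the length of radiation.

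- Section 5.7.5, closing the paragraph on HDR insertions: "Radiation therapy must be completed within 6 weeks of its initiation".
- Section 5.7: "Radiation therapy must be completed within 60 days of initiation".
- Section 5.7.3, compliance table, row "Overall Treatment time": up to 60 days is per protocol, up to 66 days is an acceptable variation, and anything longer is an unacceptable deviation.

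The schedule comes from these passages:

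- Section 5.7 gives 45 Gy in 25 fractions, Monday to Friday. For the simultaneous integrated boost, "the primary target will receive 47.6 Gy in 1.7 Gy/fraction", which the dose table in 5.7.5 lists as 28 fractions. "A three consecutive day parametrial boost may be optionally given in the sixth week" (5.7.5).
- The Point A table in 5.7.5 pairs both 45 Gy and 47.6 Gy with 4 or 5 HDR fractions.
- Section 5.7.5 also sets spacing: insertions generally start in week 4, at least 48 hours apart, and "no more than 2 insertions should be performed per week". "External beam radiation and brachytherapy may not be administered on the same day".
- Section 5.7 describes external beam "followed by low dose rate (LDR) or high dose rate (HDR) brachytherapy". Section 5.7.1 says HDR is for all patients, with exceptions documented. Section 5.4 writes brachytherapy as +/-. Section 5.6 plans Monday-to-Friday delivery over roughly six weeks, possibly including brachytherapy.

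Section 16.1.1 counts failure to complete chemoradiation within 8 weeks as a feasibility failure. More than 2 of 8 patients in cohort 1, or more than 1 of 4 in cohort 2, makes the treatment not feasible. It does not mention brachytherapy or name the day on which the 8 weeks begin.

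**The concern.** The two mandatory sentences share the same subject and the same starting point but set different limits. A site, a monitor and an analyst could each classify a finish in the seventh or eighth week differently, and all could cite the protocol.

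The 6-week sentence also has to be compatible with the fractionation that the same section prescribes. If it is not, some planned courses breach it on their first day of planning, before any delay.

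Completion time also feeds the feasibility rule in 16.1.1. That rule turns on very small counts, and the cohort 2 review must be finished before cohort 3 enrolls. It therefore matters whether brachytherapy belongs to the chemoradiation being timed.

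**Working it through.** **Day count.** Day 1 is the first fraction, so 6 weeks end on day 42 and 8 weeks on day 56. A finish on day 44 is 43 elapsed days, over 42 on either count.

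**Step 1: fraction counts, reproducing the plan's own figure.**
- 45 / 1.8 = 25 fractions.
- 47.6 / 1.7 = 28 fractions, as printed in the 5.7.5 dose table.
- (45 + 5.4) / 1.8 = 28 fractions with the parametrial boost.

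**Step 2: capacity of six weeks.** Any 42-day window holds 6 × 5 = 30 weekdays. Each HDR insertion needs its own day:
- 25 + 4 = 29 and 25 + 5 = 30 weekdays: fit.
- 28 + 4 = 32 and 28 + 5 = 33 weekdays: do not fit.

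**Step 3: earliest finish.** Rules: Monday start, weekdays only, no shared day, insertions at least 48 hours apart, at most 2 per week.

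| External beam + HDR | Interleaved from week 4 | HDR after external beam |
|---|---|---|
| 25 + 4 | day 39 | day 45 |
| 25 + 5 | day 40 | day 50 |
| 28 + 4 | day 44 | day 50 |
| 28 + 5 | day 45 | day 52 |

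External beam alone ends on day 33 (25 fractions) or day 38 (28 fractions). Over all weekday starts, the interleaved 28-fraction courses end on day 44 to 47. A Tuesday start puts 25 + 5 on day 42, with no slack.

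Against 42 days, with a Monday start, interleaved 28-fraction courses are 44 − 42 = 2 to 45 − 42 = 3 days over. Sequential ones are 50 − 42 = 8 to 52 − 42 = 10 days over. Sequential 25-fraction courses are 3 to 8 days over.

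**Step 4: the 8-week criterion.** Suppose five weekdays are lost without a 7-day hold: one gap on days 11 to 16 (four weekdays) plus day 22.

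| Course | Interleaved | HDR after external beam |
|---|---|---|
| 25 + 4 | day 46 | day 52 |
| 25 + 5 | day 47 | day 57 |
| 28 + 4 | day 51 | day 57 |
| 28 + 5 | day 52 | day 59 |

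For the last entry, external beam ends on day 45 and the insertions fall on days 46, 50, 52, 57 and 59. Day 59 is within 60 days and over 56 on either day count. Day 57 is 56 elapsed days, so it is over 8 weeks only on the inclusive count. If brachytherapy does not count, external beam ends on day 40 to 45 and every case is inside 8 weeks.

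**Sensitivity: separate nodal boost.** Section 5.7.5 allows a nodal boost after 45 Gy to a final 54 to 59.4 Gy but gives no fraction size. Assuming 1.8 Gy, it adds 9 / 1.8 = 5 to 14.4 / 1.8 = 8 fractions, or 30 to 33 in all. External beam then ends on day 40 to 45. With HDR and no interruption, the finish is day 46 to 52 interleaved or day 52 to 59 sequential. The conclusion does not rest on this case.

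**The case against.** The two limits are nested upper bounds, and finishing by day 42 satisfies both. A reader might infer that no site can follow both, but interleaved 25-fraction courses end on day 39 or 40. The disagreement concerns finishes on days 43 to 60.

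A reader might also infer that every 28-fraction course breaches the 6-week limit. The documents do not support that. Brachytherapy is optional in the cohort definitions and can be omitted with a documented reason. LDR is named in 5.7 without an insertion count. Weekend HDR is not expressly barred and would bring 28 + 4 to day 40 and 28 + 5 to day 41. On the other side, 5.7.1 makes HDR the rule, the Point A table pairs 47.6 Gy with 4 or 5 insertions, and 5.6 plans Monday-to-Friday delivery. The conflict therefore stands for 28 fractions with weekday HDR.

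On 16.1.1, the general instruction to start HDR in week 4 points to interleaving, where even five lost weekdays leave the finish inside 8 weeks. The start date can be inferred, because 5.6 starts cisplatin on day 1 of radiation. Sections 5.4 and 5.6 lean towards treating brachytherapy as part of chemoradiation. An 8-week endpoint stricter than a 60-day compliance limit may be deliberate and is not in itself an error. All of this narrows the secondary point to a missing definition.

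**Conclusion.** The contradiction is explicit: under 5.7 and 5.7.3 a finish on days 43 to 60 is compliant, and under 5.7.5 it is a breach. The three passages must be reconciled. Which limit is clinically right is not a question for this review.

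The 6-week limit is also unattainable for 28 external-beam fractions with 4 or 5 HDR insertions. The shortfall is 2 or 3 weekdays of capacity, and the earliest finish is day 44 or 45. This assumes weekday-only HDR, separate days for the two modalities and no interruption.

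The gap in 16.1.1 is secondary. Among the 25- and 28-fraction courses, brachytherapy's status changes a patient's classification only when HDR follows external beam and several weekdays are lost. Only 28 + 5 (day 59) then exceeds 8 weeks on either day count. A reader might infer that this ambiguity will stop cohort 3. The documents do not support that. They give no completion-time rates, and one reclassified patient would decide the matter only alongside one other failure in cohort 2 (or two others in cohort 1).

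**What to change.** Reconcile sections 5.7, 5.7.3 and 5.7.5 to one completion limit chosen by the sponsor. Before adopting it, check it against the fraction counts, the number and spacing of HDR insertions and the bar on same-day treatment, and say whether it covers brachytherapy.

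In section 16.1.1, state the day on which the 8-week clock starts, how days are counted, whether brachytherapy is part of the chemoradiation being timed, and how the criterion relates to the compliance table in 5.7.3. If it is meant to be stricter than that table, say so.

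The cost is amendment wording. No patients, visits or procedures are added.

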5.7.6 Treatment planning priorities and instructions

Critical structures and target priorities are listed in order of decreasing importance:

EBRT

1. Bowel
2. Bone marrow
3. Rectum
4. Bladder
5. Femurs

If max dose constraints are exceeded, the following solution can be entertained: For conventional RT with 3D planning, use the field in field technique to decrease hot spots and to reduce the bowel dose when MLCs are used.

Brachytherapy

1. Rectum
2. Bladder
3. Sigmoid

If dose constraints of critical structures are exceeded, the following solution can be entertained: For volume-directed brachytherapy, if the treatment planning system provides a manual optimization option, optimize the plan manually to reduce dose to the critical structures as long as D90 of CTV meets target volume constraints.

5.7.7 Dose Calculations

The primary data set for dose calculations is CT. In the case in which contrast is present during the treatment planning CT, the density of the contrast should be overridden to a representative background electron density. Heterogeneity corrections should be applied. The dose grid size should be ≤ 3 mm in all directions, which means that the CT slice thickness should be ≤ 3 mm.

For IMRT plans, patient specific QA is required. QA is performed by delivering the plan onto a phantom and measuring the dose using an ion chamber array or other 2D/3D device. Measured dose distribution will be compared to planned dose distribution using a Gamma criterion of 3% dose difference and 3 mm distance to agreement. The pass rate should be at least 90% measured

BrUOG 355: 7/8/17, 7/11/17, 7/20/17, 8/7/17, 8/8/17, 8/14/17, 8/16/17, 8/21/17, 8/22/17, 8/24/17, 8/28/17, 9/5/17, 9/6/17, 9/8/17, 9/11/17, 11/7/17, 11/8/17, 11/19/17 approved DD, 11/20/17, 12/12/17, 12/14/17, 1/29/18, 2/1/18, 2/6/18, 2/7/18, 2/8/18, 2/9/18, 2/12/18, 2/13/18, 3/8/18 all reviews, 3/9/18, 3/13/18, 3/14/18, 3/15/18, 4/19/18, 4/23/18, 5/29/18, 6/5/18, Amendment # 1 7/9/18, Amendment # 2 12/12/18, Amendment #3, 4/6/2020, Amendment #4 5/11/2020

for the entire plan.

5.7.8 Daily treatment localization/Image-guided radiation therapy (IGRT)

Conventional RT (4-field box)

Skeletal imaging using an electronic portal imaging device (EPID) or film portal imaging should be performed at least weekly to verify setup accuracy. IGRT technique such as orthogonal kV or volumetric imaging such as Cone Beam CT (CBCT) can also be used for weekly setup verification.

IMRT

Daily IGRT is required for this protocol when the IMRT treatment technique is used. Any form of online imaging is acceptable, such as MV or kV planar imaging, MVCT or MV CBCT, kV CBCT, CT on rails, etc. The AAPM recommendations stated above for verifying coincidence of the imaging and treatment beam reference points must be adhered to for daily use of IGRT. At the time of simulation, it is recommended to place the isocenter along the patient's midline 1.5 cm caudal to the inferior border of the sacroiliac joint. In general, the CT or CBCT will be used for setup verification using bone landmarks only and not for soft tissue alignment. Small soft tissue shifts (≥ 3 mm) are acceptable. Otherwise, the treating physician may elect to postpone treatment or re-simulate.

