5.7.2 Immobilization and simulation

Conventional RT

CT simulation is required. Field outlines should be drawn electronically on Digitally Reconstructed Radiographs (DRRS) produced from the CT simulation information. Localization or block-check-images of simulated fields are to be obtained in a simulator and/or treatment machine. Digital pictures of all treatment portals with the patient in the treatment position are to be submitted for quality assurance review. All treatment fields, whether formed by cerrobend blocks or multi-leaf collimation, should be independently checked against the corresponding DRRs. Prone positioning with bowel exclusion devices (e.g. belly boards) is allowed.

3D planning is at the physician's discretion. If 3D planning is being done, a CT simulation scan is required with a slice thickness ≤ 3.0 mm for the regions extending at least 4cm above and below target volumes. Patients can be simulated supine or prone. All subjects will have a customized immobilization device (e.g., Alpha Cradle or Vac-Loc) fabricated at the time of simulation. A full bladder is required at the time of simulation and treatment. Intravenous contrast is recommended to visualize vessels better. Oral or rectal contrast is not recommended for treatment planning.

IMRT

All subjects will undergo a CT (or PET/CT) simulation scan in the supine position using a slice thickness ≤ 3.0 mm and large field-of-view pelvic protocol. A customized immobilization device fabricated at the time of simulation is required. It is recommended that CT scans be obtained from the T12 vertebral body to 5 cm below the ischial tuberosities. For patients undergoing CBCT with each fraction, it is recommended that the isocenter be placed along the patient's midline 1.5 cm caudal to the inferior border of the sacroiliac joint. Otherwise, isocenter

BrUOG 355: 7/8/17, 7/11/17, 7/20/17, 8/7/17, 8/8/17, 8/14/17, 8/16/17, 8/21/17, 8/22/17, 8/24/17, 8/28/17, 9/5/17, 9/6/17, 9/8/17, 9/11/17, 11/7/17, 11/8/17, 11/19/17 approved DD, 11/20/17, 12/12/17, 12/14/17, 1/29/18, 2/1/18, 2/6/18, 2/7/18, 2/8/18, 2/9/18, 2/12/18, 2/13/18, 3/8/18 all reviews, 3/9/18, 3/13/18, 3/14/18, 3/15/18, 4/19/18, 4/23/18, 5/29/18, 6/5/18, Amendment # 1 7/9/18, Amendment # 2 12/12/18, Amendment #3, 4/6/2020, Amendment #4 5/11/2020

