placement is left to the discretion of the treating physician. It is recommended to use a consistent bladder filling state (e.g. always full or always empty) for simulation and treatment. It is recommended for patients not to be simulated or treated with a full rectum as this may result in poor setup reproducibility. Bowel preparatory agents (enema, stool softeners, etc.) may be applied at the discretion of the physician. Oral contrast is optional. Radio-opaque cervical markers or implanted fiducials are optional

The volume irradiated will include the totality of the gross disease locally and regionally, as visualized by CT scan, the whole uterus, paracervical, parametrial and uterosacral ligaments as well as the areas of the obturator, hypogastric, external and internal iliac lymph nodes. In patients treated with extended fields the para-aortic regions with a minimum margin of 2 cm should be included. A margin of 2-3 cm should be given around the gross disease and 1.5-2 cm around uninvolved lymph nodes.

Brachytherapy

For 3D brachytherapy planning, all subjects will undergo a CT (or PET/CT) simulation scan using a slice thickness ≤ 3.0 mm with brachytherapy applicators and dummy sources in. It is recommended that CT scans contain the entire brachytherapy applicators and the critical structures such as bladder and rectum.

Maintaining applicator position is required from the time of applicator insertion to simulation and treatment. Before a CT scan, a Foley catheter is inserted into the bladder and the balloon must be filled with 7 cc of radio-opaque fluid to define the bladder reference point in treatment planning.

For volume-directed brachytherapy, pelvic MRI (≤ 3 mm slice thickness) is required with either the first or second insertion. An MRI-compatible applicator is required to perform volume-directed brachytherapy. Subsequent insertions may use CT or MRI for planning.

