5.7.9 Re-planning

Re-planning (such as to account for changes in tumor volume) is allowed. If re-planning is necessary, the new treatment plan should meet the same criteria as the initial plan, as if the new plan were delivered for the entire treatment course. The new treatment plan should be submitted for central review according to the same process as the initial plan.

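### Section 5.7.8: the 3 mm soft tissue tolerance for daily IMRT set-up has its inequality reversed, so it accepts shifts of 3 mm or more and escalates smaller ones

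*Combined protocol and SAP*

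**What the plan says.** Section 5.7.8 (IMRT) makes image guidance compulsory at every fraction. It first sets the alignment method: "In general, the CT or CBCT will be used for setup verification using bone landmarks only and not for soft tissue alignment". The tolerance follows: "Small soft tissue shifts (≥ 3 mm) are acceptable. Otherwise, the treating physician may elect to postpone treatment or re-simulate". It does not say which tissue is meant, or whether a shift is the displacement left after bone alignment or a couch correction made to match soft tissue.

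Two other places bear on soft tissue position, and neither gives a number for it:

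- Section 5.7.2 (IMRT) recommends consistent bladder filling and adds: "It is recommended for patients not to be simulated or treated with a full rectum as this may result in poor setup reproducibility".
- Section 5.7.9 says: "Re-planning (such as to account for changes in tumor volume) is allowed". It sets no numeric trigger.

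**The concern.** A tolerance rule of this kind should pass small shifts and send larger ones to the physician. The printed sign does the reverse. Because no other section supplies a soft tissue tolerance, the reader cannot correct the rule from elsewhere in the document.

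What is at stake is a treatment-delivery instruction in a curative-intent regimen. A site following the text literally, or an auditor checking compliance against it, would be working from a backwards rule.

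**Working it through.** No sample size, error rate or event count is involved. The check is a reading of the rule and its complement, followed by a count of the inequality signs in section 5.7.

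**1. The rule and its complement**

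| | Accepted | Physician may postpone or re-simulate |
|---|---|---|
| As printed (≥ 3 mm) | shift ≥ 3 mm | shift < 3 mm |
| With the sign reversed (≤ 3 mm) | shift ≤ 3 mm | shift > 3 mm |

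Under the printed number, a 1 mm shift falls in the right-hand column and a 20 mm shift in the left. Only the unquantified word *small* stands against accepting 20 mm. With the sign reversed, both sentences make sense together.

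**2. Does another meaning of *shift* rescue the text?**

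- *Residual displacement after bone alignment.* The larger displacement passes and the smaller one is escalated. The rule is backwards.
- *Couch correction to soft tissue.* Corrections of 3 mm or more pass, and corrections under 3 mm lead to postponement or re-simulation. It is still backwards.
- *3 mm as the level at which a correction is made, with the word* small *as the cap.* The second sentence would then have to refer to shifts that are not small, and no number defines those. The rule has no usable upper threshold.

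**3. Sign count in section 5.7**

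| Sign | Where | Count | Fits its sentence |
|---|---|---|---|
| ≤ | 5.7.2, slice thickness (3.0 mm three times, 3 mm once) | 4 | 4 |
| ≤ | 5.7.3, overall treatment time (60 and 66 days) | 2 | 2 |
| ≤ | 5.7.7, dose grid and slice thickness (3 mm) | 2 | 2 |
| ≥ | 5.7.5, PTV coverage doses (three table rows) | 3 | 3 |
| ≥ | 5.7.8, soft tissue shift (3 mm) | 1 | 0 |
| Total | | 4 + 2 + 2 + 3 + 1 = 12 | 11 |

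The signed 3 mm limits number 4 + 2 + 1 = 7. Six use ≤, and the one in 5.7.8 uses ≥. Examples in the right direction are "simulation scan in the supine position using a slice thickness ≤ 3.0 mm" and "pelvic MRI (≤ 3 mm slice thickness) is required with either the first or second insertion" (both 5.7.2), "The dose grid size should be ≤ 3 mm in all directions" (5.7.7) and, for the opposite sign, "Exactly 95% of PTV receives ≥ 45 Gy" (5.7.5). The two signs are kept apart elsewhere, so a systematic conversion fault is unlikely. One misread character remains possible.

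**4. Size against the planning margins**

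Section 5.7.3 expands the target by 15 mm around tumor, cervix and uterus, 10 mm around parametria and vagina, and 5 mm around nodes and boost volumes. If *shift* means residual displacement, the printed rule would accept movement beyond the 5 mm expansion, while ≤ 3 mm stays inside it (3 < 5). If it means a couch correction, the comparison does not apply.

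**The case against.** The strongest objection is that everything rests on one character in text taken from a PDF. In the same section, the boost row of the 5.7.5 table is visibly garbled: an equals sign stands where a range dash belongs, and its upper dose is 58.4 Gy against 59.4 Gy in the dose column. The count of 12 includes that row. This stands as a reason to check the source page. It does not make the printed rule coherent.

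Second, the six other 3 mm limits concern slice thickness or dose grid, not set-up. That is true: they show that ≤ is reproduced correctly nearby, but they do not show what was intended in 5.7.8. The case for reversal rests on the sentence itself.

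Third, *small* is a bound of a sort, and the text could be read as allowing modest corrections once an offset reaches 3 mm, as an exception to bone alignment. That reading is possible but strains the second sentence and still leaves no numeric ceiling.

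Fourth, the plan has other protection: the 10 and 15 mm expansions, and an optional internal target volume built from full- and empty-bladder scans with a 7 mm margin. These absorb motion but are not set-up tolerances.

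Finally, nothing proves that 3 mm is the intended ceiling. With ≤ 3 mm, a cervix or uterus shift of 4 to 14 mm would go to the physician although it lies inside the 15 mm margin. This stands, and it is why the value needs clinical confirmation.

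**Conclusion.** The concern holds: the sentence is wrong as written. One of 12 signs in section 5.7 conflicts with its own sentence, and it turns the document's only soft tissue tolerance from an upper bound into a lower bound.

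The severity is minor. Accepting a shift and electing to postpone are both permissive terms, and clinicians would probably apply ≤ 3 mm anyway. The share of patients treated with IMRT is not stated, so exposure to the rule cannot be sized. No effect on the feasibility criteria, sample size or analyses is claimed.

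The conclusion assumes that the source page also prints ≥. That 3 mm is the intended limit is inferred by keeping the printed number; a strict < 3 mm would also make the two sentences agree.

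**What to change.** Check the sign on the source page of section 5.7.8. If it is ≥, change the tolerance to ≤ 3 mm, so that shifts above 3 mm go to the treating physician's decision to postpone or re-simulate. The radiation oncology lead should confirm the value. The cost is a one-character correction in the next protocol revision.
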